2.3 Known and potential risks and benefit for the study subjects

2.3.1 Risks and inconveniences related to participation in the study

ARs related to administration of the test drug and characteristic for the group of p38 MAPK inhibitors may be observed as well as AR not previously noted (known ARs during treatment with p38 MAPK inhibitors are provided in section 2.2.2.) may be noted during this study. Safety profile of p38 MAPK inhibitors is satisfactory even during systemic use, and considering the absence of Seroguard absorption from the abdominal cavity according to pre-clinical data, it is possible to calculate good tolerability of the drug. Based on results of the Phase I clinical study, safety profile of the drug Seroguard was comparable to that of placebo. Thus, AR incidence in the group of treatment with the test drug is expected not to exceed the similar parameter in the placebo-control group (risk related to the underlying disease which is an indication for surgery, risk of surgery and anesthesia).

Blood sampling for clinical laboratory investigations (see section 4.2.3.5) may be accompanied by mild pain which is fleeting and/or ecchymoses may be formed at the site of needle injection. A thrombus may be formed in vein or infectious complication may be developed significantly rarer. Dizziness and/or fatigue may be observed during and soon after blood sampling.

Electrocardiographic examination (see section 4.2.3.6) is a painless examination, however rash or irritation may develop on patient's skin at the sites of gel application and using sticky electrodes for ECG.

Ultrasound investigation (see section 4.2.3.6) – In the present study, USI of the abdominal cavity is performed by transabdominal access and USI of the pelvis - by transvaginal access. The latter may be accompanied by mild painful sensations.

Hysterosalpingography. Rare complications of performing HSG include development of acute or chronic endometritis (in cases when bacteria along with contrast agent get from vagina into the uterine cavity), as well as allergy to contrast agent (contrast contains iodine, that's why presence of allergy to iodine should be specified in all women before HSG). Exceedingly rare complication of HSG is injury of fallopian tubes and/or uterine. In addition, during HSG a woman receives a small dose of X-ray irradiation (control of maximum individual effective irradiation dose is required).

Study procedures performed under the protocol, including blood sampling and electrocardiographic investigation, are routine in general clinical practice. Frequency of their performance does not make any significant additional load for female patient.

In order to minimize risks, the study will include female patients meeting inclusion criteria (section 5.1) and not having non-inclusion criteria (section 5.2). All the study subjects before signing informed consent to participate in the given study will be informed on possible risks and discomfort as well as on necessity to inform the Medical Investigator on health problems, if any. Medical Investigator will perform close monitoring of the study participants during the study. If necessary (for example, development of ARs), Medical Investigator will take required measures to perform respective investigations and/or administration of the therapy required.

2.3.2 Possible benefit related to participation in the study

In the study, no money compensation is planned for female patients, however, they will have possibility to take adequate treatment and investigation under the protocol. Decreased incidence, prevalence and severity of adhesions in abdominal cavity as a result of administration of the study drug, i.e. reduced risk of developing post-surgical complications related to adhesive process, which increases chances of becoming pregnancy and/or reduces probability of pelvic adhesions, is possible (but not obligatory) during the study.

Throughout the study, female subjects of the study will be under close control of employees of healthcare institution participating in conducting the study.

Considering the above, as well as pre-clinical data on safety of the drug Seroguard, the results of the Phase I clinical study and clinical data on administration of p38 MAPK inhibitors, risk/benefit ratio in the present study may be considered to be acceptable for patients who will participate in it.

2.4 Description and justification of route of administration, dosages, dosage regimen and therapy course

The test drug Seroguard is administered once into serous cavity in aseptic conditions before completion of surgery. Repeated administrations are not recommended. The drug is ready for administration. Before administration, aspirate all the remaining liquids from serous cavity (blood, exudates, solutions administered intraoperatively). Before use, heat the drug to body temperature. After an adequate sanitation of the abdominal cavity with warm normal saline in the quantity of 100 mL, the drug Seroguard, solution in the concentration of 0.41 g/L is administered through trocar with the help of a metal tube 25 cm long with inner diameter of 4 mm with a silicone nozzle 5 cm long, which is tightly connected to Janet syringe containing an anti-adhesion solution/placebo.

The study drug shall be applied onto the operated surface in the quantity of 2.4 mL/kg body weight or 1.5 mL/kg body weight by means of forced pressing the plunger of the syringe.

In order to create the maximum afflux of anti-adhesion agent into the pelvis, all the patients should be recommended to practice active behavior (getting up and walking) in the end of the first day after the surgery and supine position with the head kept up by the bed head elevation during rest.

At the post-operative period, for all the groups patient management is performed in accordance with the established standards.

The drug is intended only for administration into serous cavity, intravenous administration is unacceptable. Do not mix with other drugs. Do not use as a vehicle of other drugs as antibiotics, chemotherapeutic agents, etc.

Selection of dosage is based on principle of Seroguard action – the drug acts at the site of its administration. Seroguard should cover the surface of abdomen in order to form an efficient liquid barrier which causes launch of apoptosis of activated fibroblasts, interrupting development of adhesive process at the site of abdomen injury.

In the studies by diZerega (22,23), area of abdomen and volume of liquid required for its complete coverage were determined. For a human being, a maximum weight coefficient is approximately 2.4 mL/kg (that is, for patient with weight of 80 kg, $80 \times 2.4 = 192$ mL minimum). Thickness of boundary layer, in which reaction to injury is developed, which causes adhesions, and in which it is necessary to block activity of kinase cascade, is about $h = 0.3$ mm based on morphometry data. Thus, the volume of boundary layer is equal to multiplication of thickness of boundary layer by area of abdomen surface ($V = S \times h$). Activity of cascades in cells of deeper layers is unfavorable to be suppressed, because of ongoing process of surgical wound healing.

For gradually released active component of IC_{50} value related to MAPK p38 fibroblasts, $IC_{50} = 300$ nM, $M = 413.9$ g ($IC_{50} = 413.9 \times 300 \times 10^{-9} = 0.00012417$ g/L = 0.12417 mg/L) (24).

Area of abdomen (approximately equal to body surface) of a person with weight of 80 kg and height of 180 cm is about 2 m². Volume of boundary layer is $2 \times 0.0003 = 0.0006$ m³ = 0.6 dm³ (the drug will be distributed at this volume).

Based on $T_{1/2}$ coding RNA for MAPK (25) for 3-day exposure (based on absence of active absorption of conjugate in abdominal cavity):

$$0.12417 \text{ mg/L} * 0.6 \text{ L} * 24 = 1.79 \text{ mg}$$

Considering additional 10 % (200 mL of liquid is administered), a dose administered should be $1.79 \times 1.1 = 1.997$ mg. Thus, for a person with weight of 80 kg and height of 180 cm, a quantity of the conjugate administered should contain about 2 mg of the drug, and the volume should be about 200 mL, which is 2.4 mL/kg. Efficacy and safety of the dose 1.5 mL/kg will be also evaluated in the study considering that the drug will exert its action not on the whole surface of the abdomen, but mainly in the pelvis.

Maximum dose administered to rats in the toxicological study is 30 mL/kg intravenously and intraperitoneally, meanwhile neither death of animals, nor abnormal general condition or behavior of animals were noted. In the study in dogs, the maximum administered dose of Seroguard was 12 mL/kg intraperitoneally, whereby no abnormal functioning of organs and systems of animals was observed. After recalculation for human being (26), both dosages exceed the above doses for the Phase II study for at least twice.

Sodium chloride, solution for infusion 0.9% (CJSC EAST-PHARM, Russia) was selected as the placebo). Selection of the drug is based on requirements to placebo in the given study:

- The drug may be used for irrigation of the abdominal cavity during the surgery;

- The drug does not exert effect on the body of patient after selected route of administration in the dosage selected.

Sodium chloride solution is widely used in abdominal surgery as placebo (27,28,29,30), it does not also exert significant pharmacological action and may not influence on parameters of safety of patients, that's why its use as a placebo is justified.

2.5 Normative-regulatory base for conducting the clinical study

The present document is a protocol of a clinical study which is planned to be conducted as per the principles of Declaration of Helsinki of the World Health Association (adopted by 18th WMA General Assembly, Helsinki, June 1964, amended by 64th General Assembly, Fortaleza, October, 2013), tripartite guideline for Good Clinical Practice (ICH GCP) and is regulated by acting legislation of the Russian Federation (RF):

- Federal Law dated 12.04.2010 No 61-Φ3 “On drug circulation” as amended.
- Federal Law dated 27.07.2006 No 152-Φ3 “On personal data” as amended.
- RF national standard GOST P52379-2005 “Good Clinical Practice”.
- RF government decree No 714 dated 13.09.2010 (as amended by the RF government decree dated 18.05.2011 No 393, dated 04.09.2012 No 882) “On the approval of model rules of mandatory health and safety insurance for patients participating in a clinical drug study”.
- Order of RF Ministry of Healthcare dated 29th of November, 2012 No 986H “On approval of regulation on ethics board”
- Order of RF Ministry of Healthcare dated 01.04.2016 N 200H “On approval of Good Clinical Practice requirements”.

2.6 Description of the study population

The study population will be hospitalized patients with confirmed diagnosis of pelvic adhesions. The study will include female patients aged from 18 to 45 years after signing informed consent. Patients meeting inclusion criteria, without non-inclusion criteria (sections 5.1 and 5.2), passed all the screening procedures, will be included into the study and randomized into one of the study groups

3 Purposes and objectives of the study

3.1 Purpose

The present study is aimed at evaluating efficacy of the drug Seroguard, solution, used for prevention of pelvic adhesions.

Main purposes of the study:

Comparison of efficacy of the drug Seroguard, solution, administered in the volume of 1.5 mL/kg or 2.4 mL/kg and placebo (0.9% sodium chloride) in the volume of 1.5 mL/kg or 2.4 mL/kg by presence, severity and prevalence of adhesions during laparoscopic treatment of pelvic adhesions.

Study of safety profile of the drug Seroguard, solution administered in the volume of 1.5 mL/kg or 2.4 mL/kg, in comparison to placebo (0.9% sodium chloride) in the volume of 1.5 mL/kg or 2.4 mL/kg during laparoscopic treatment of pelvic adhesions.

3.2 Study objectives

1. To determine change in number of pelvic adhesions based on MRI data in post-surgical period in comparison to data of pre-surgical MRI data
2. To determine change in thickness of pelvic adhesions based on MRI data in post-surgical period in comparison to data of pre-surgical MRI data
3. To determine frequency of limited displaceability of pelvic organs in post-surgical period (based on results of transvaginal ultrasound investigation).
4. To determine frequency of hyperechoic linear lesions in post-surgical period based on results of transvaginal ultrasound investigation.
5. To determine changes in frequency of detecting limited displaceability in comparison to baseline (absolute change and in % of baseline value).
6. To determine changes in frequency of detecting hyperechoic linear lesions based on repeated transvaginal ultrasound investigation in comparison to baseline.
7. To determine frequency of detecting complete absence of USI – signs of adhesion process in pelvis in post-surgical period (defined as absence of limited displaceability of pelvic organs and absence of hyperechoic linear lesions)
8. To determine number of adhesions during surgery.
9. To determine number of dense adhesions during surgery.
10. To determine percentage of female patients with any adverse reactions.
11. To determine percentage of female patients with any serious adverse reactions.
12. To determine percentage of female patients with adverse reactions, relation of which to use of the test drug or the placebo is “definite”, “probable” or “possible”.
13. To determine percentage of female patients with serious adverse reactions, relation of which to use of the test drug or the placebo is “definite”, “probable” or “possible”.
14. To determine percentage of female patients with mild adverse reactions.
15. To determine percentage of female patients with moderate adverse reactions.
16. To determine percentage of female patients with severe adverse reactions.
17. To determine percentage of female patients with clinically significant changes in results of physical examination.
18. To determine percentage of patients with clinically significant changes in vital signs.
19. To determine percentage of female patients with clinically significant changes in electrocardiogram (ECG).
20. To determine percentage of female patients with clinically significant laboratory parameters.

4 Design of the study

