2.2.2 Clinical studies

Seroguard, solution is a new original drug that has passed pre-clinical studies, Phase I clinical study was also performed (19). Multi-center double-blind placebo-controlled study included patients of both genders at the age from 18 to 75 years having indications for planned laparoscopic cholecystectomy. Treatment group (Seroguard) included 24 patients, and placebo group (0.9% sodium chloride) - 23 patients. Seroguard, solution 0.41 g/L, JSC Pharmasyntez, Russia or its respective placebo were administered into abdominal cavity at the end of laparoscopic cholecystectomy at the dose of 2.4 mL/kg. Incidence, nature and severity of adverse reactions (including clinically significant abnormalities of physical examination, vital signs, instrumental investigations, clinical laboratory parameters) were evaluated. 206 adverse reactions (AR) were recorded in the study: 110 (53,4%) – in the group of treatment with Seroguard and 96 (46.6%) – in the placebo group. 14 cases of adverse reactions (6.8%) were moderate and one was severe, remaining adverse reactions were mild. 194 (94.2%) ARs were doubtfully related to administration of the drug, 8 (3,9%) – conditionally related, and 4 ARs (1,9%) in the treatment group were evaluated as possibly related to the drug administration. 196 of 206 ARs (95.2%) completed by recovery of patient, in the remaining 10 cases (4.9%), a significant amelioration was observed. 4 serious ARs were also recorded in three patients of both groups in the study.

No statistically significant changes, except for level of eosinophils and lymphocytes in the placebo group, were recorded in most of complete blood count and blood chemistry parameters. A statistically significant elevation ($p = 0.0297$) was noted in the level of eosinophils in the placebo group by Visit 11 (Day 28), however, it was not clinically significant. Similarly, elevation in lymphocytes ($p = 0,0148$) was observed by Visit 11 (Day 28), which was not clinically significant.

The performed analysis of coagulogram data did not reveal statistically significant differences in any parameter between the Visits ($p > 0.05$). Analysis did not also show any statistically significant variations in vital signs ($p > 0.05$).

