9.1.4 Safety analysis

Descriptive part of safety analysis by primary endpoint will include evaluation of frequencies and bilateral 95% CI for the following primary endpoint parameters:

- AR – common frequency and frequency in separate groups (as per ICD-10)
- SAR - common frequency and frequency in separate groups (as per ICD-10)
- Frequency of clinically significant changes in results of physical examination – in general, for the study and by visits
- Frequency of clinically significant changes in parameters of laboratory investigations – in general, for the study and by visits
- Frequency of clinically significant changes in parameters of BP and heart rate – in general, for the study and by visits
- Frequency of clinically significant changes in ECG parameters – in general, for the study and by visits

Comparison of frequencies between main and control groups will be performed using Fisher's exact test (bilateral variant).

Analysis of the specified safety parameters will be performed for ITT and safety population (if it is different from ITT).

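### The adverse-reaction objectives and section 9.1.4 count women with a reaction, never reactions per woman, so the any-reaction and mild-reaction percentages are likely to respond poorly to a heavier total burden

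*Protocol*

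**What the plan says.** Section 3.2 lists the objectives. Objective 10 is "To determine percentage of female patients with any adverse reactions". Objectives 11 to 16 ask in the same form for the percentage of women with serious, related, related serious, mild (14), moderate (15) and severe (16) reactions. Objectives 17 to 20 do so for clinically significant examination, vital-sign, ECG and laboratory changes.

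Section 9.1.4 plans the frequency of adverse and serious adverse reactions, overall and by ICD-10 group, and the frequency of clinically significant abnormalities overall and by visit. It then says "Comparison of frequencies between main and control groups will be performed using" a two-sided Fisher's exact test. Neither section names a count or rate of reactions per woman.

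The protocol's only clinical data on how often reactions occur are in section 2.2.2: "Treatment group (Seroguard) included 24 patients, and placebo group (0.9% sodium chloride) - 23 patients", and "206 adverse reactions (AR) were recorded in the study: 110 (53,4%) – in the group of treatment with Seroguard and 96 (46.6"%, the last figure being the placebo share. On severity: "14 cases of adverse reactions (6.8%) were moderate and one was severe, remaining adverse reactions were mild". Section 2.2.2 does not give the percentage of patients who had at least one reaction.

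Section 8.3 records each reaction separately, with its nature, grade, causality, start and stop times and outcome. Section 8.4 asks for a new form when a continuing reaction is reported again.

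**The concern.** A yes/no summary per woman loses information once most women have several reactions: a woman with two and a woman with eight count the same. Phase I averaged more than four per patient in both arms, nearly all mild. If anything similar happens here, objectives 10 and 14 will be high in every arm and will barely move when the drug adds reactions. A finding of no difference from placebo on these two measures would then say little about total burden. Safety against placebo is one of the two main purposes in section 3.1.

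**Working it through.** **Inputs.** From section 2.2.2: 110 reactions in 24 Seroguard patients, 96 in 23 placebo patients, 14 moderate and 1 severe. From section 4.3.1: 26 randomised per arm. From sections 9.1.4 and 9.3: two-sided Fisher's exact test at 5%. Assumed, because the protocol gives no figure: the distribution of reactions across patients, the rate in this trial, and a doubled burden as the effect to detect.

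**1. The protocol's figures reproduce.** 110/206 = 53.4%; 96/206 = 46.6%; 14/206 = 6.8%. Mild: 206 − 14 − 1 = 191 (92.7%).

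**2. Reactions per patient.** Seroguard 110/24 = 4.58; placebo 96/23 = 4.17; mild, both arms pooled, 191/47 = 4.06.

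**3. Implied percentage with at least one reaction.** For mean m this is 1 − exp(−m) with no clustering (Poisson), or 1 − (k/(k+m))^k for a negative binomial, where smaller k means stronger clustering. At m = 4.17: 98.5% (Poisson), 90% (k = 2), 81% (k = 1), 67% (k = 0.5). At m = 4.58: 99.0%, 91%, 82%, 69%. For mild reactions (m = 4.06): 98%, 89%, 80%, 67%.

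**4. Power when one arm has twice the reactions, 26 v 26.** Fisher power is by exact enumeration. The rank-sum test on counts was simulated (4,000 runs per setting, error about one percentage point). The rate-ratio column is Φ(ln 2/SE − 1.96), with SE² = [(1/(2m) + 1/k) + (1/m + 1/k)]/26 and 1/k = 0 for Poisson. For m = 4.17 and k = 1, SE² = (0.120 + 1 + 0.240 + 1)/26 = 0.0907, SE = 0.301, and power = Φ(0.34) = 63%. That column treats k as known, so it is somewhat optimistic.

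| Mean on placebo | Clustering | Any reaction, placebo v drug | Fisher | Rank test on counts | Rate ratio |
|---|---|---|---|---|---|
| 4.17 | Poisson | 98.5% v 99.98% | 0% | 100% | 100% |
| 4.17 | k = 2 | 90% v 96% | 2% | 76% | 86% |
| 4.17 | k = 1 | 81% v 89% | 7% | 49% | 63% |
| 4.17 | k = 0.5 | 67% v 76% | 6% | 26% | 40% |
| 2 | Poisson | 86% v 98% | 10% | 98% | 98% |
| 2 | k = 2 | 75% v 89% | 16% | 66% | 76% |
| 2 | k = 1 | 67% v 80% | 12% | 45% | 57% |
| 2 | k = 0.5 | 55% v 67% | 9% | 24% | 37% |
| 1 | Poisson | 63% v 86% | 37% | 81% | 82% |
| 1 | k = 2 | 56% v 75% | 23% | 52% | 61% |
| 1 | k = 1 | 50% v 67% | 16% | 36% | 47% |
| 1 | k = 0.5 | 42% v 55% | 9% | 23% | 33% |

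The count comparison is more powerful in all 12 settings. Repeat simulations put the weakest one at 22 to 23%, hence the range of about 22 to 100%.

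**5. Pooled placebo.** If the two placebo arms are combined (26 v 52), Fisher power for a doubling at the Phase I rate is still only 0 to 11%.

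**6. Do the other objectives fill the gap?** Moderate or severe reactions numbered 15 in 47 patients, so at most 15/47 = 32% of patients had one. That is well away from any ceiling. If this rate (0.32 per patient) doubled, Fisher power on the percentage would be about 14% (k = 1) to 24% (Poisson). These objectives can show more severe or more drug-related reactions. They do not measure the total, of which 93% was mild in Phase I.

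**The case against.** **Safety is not reduced to one measure.** A reader might infer that objectives 10 and 14 are the whole safety assessment, or its headline. The protocol does not support that. Objectives 11 to 13 and 15 to 20, the ICD-10 breakdown, and the unexpected reactions and withdrawals in section 4.1 cover seriousness, relatedness, severity, type and abnormalities. No section ranks objective 10 above the rest. What the two percentages mainly miss is extra mild reactions, which section 8.2 defines as easily tolerated and needing no special treatment. This stands and limits the weight of the point.

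**The ceiling is inferred, not documented.** A reader might infer from the Phase I means that nearly every woman will have a reaction. That is only the no-clustering end of a range starting near 67%. Phase I also differed: cholecystectomy, both sexes, ages 18 to 75, and closer observation (section 2.2.2 refers to the "level of eosinophils in the placebo group by Visit 11 (Day 28"), against three visits from surgery onward here. At 1 reaction per woman the figure is about 42 to 63%. This also stands, but the loss of power persists at those lower rates.

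**Doubling is a chosen effect.** The Phase I ratio was 4.58/4.17 = 1.10. At that ratio even an unclustered rate comparison, 26 v 26, has about 11% power. At a 1.5-fold burden and the Phase I rate, the rate comparison has 17 to 90% against 0 to 4% for Fisher. Counts are more sensitive but do not remove the limit set by small arms.

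**The analysis plan may add counts.** Section 9.1 calls its own description brief and defers the complete analysis; it also promises absolute frequencies. So one cannot say that the detailed records are discarded. But the protocol is not simply silent: it fixes every reaction objective as a percentage of women, and Fisher's test needs one yes/no value per woman.

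**Conclusion.** The point holds as a modest improvement to the analysis, not as an error. The protocol sets a yes/no form for all reaction objectives and for the comparison in 9.1.4. On its own Phase I figures, the any-reaction and mild-reaction percentages are likely to be high in every arm and insensitive to total burden. For a doubled burden at 26 v 26, Fisher power on any reaction is about 0 to 7% at the Phase I rate and 9 to 37% at 1 to 2 reactions per woman, against about 22 to 100% for counts.

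The sizes rest on assumed clustering (Poisson to k = 0.5), an assumed rate for this trial and a hypothetical doubling. The direction held in every setting tried. The documents do not show that safety as a whole goes unmeasured, that the percentages will be close to 100%, or that Seroguard doubles reactions.

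**What to change.** In section 9.1.4, keep the planned percentages and add the number of distinct adverse reactions per woman, for all reactions and for Grade 2 or higher. Compare each Seroguard arm with placebo by a rate ratio with 95% CI from a negative binomial model. Count a continuing reaction that is re-reported on a new form under section 8.4 once. Settle this before unblinding.

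The cost is one extra safety table from data already recorded under section 8.3, with no change to conduct. The downsides are that repeat reports must be linked before counting, and that under strong clustering the comparison is only moderately powered, so the interval should be read rather than the p-value alone.
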